### (3) Follow-up in the Queue:

- 1) follow-up time: 3 years after discharge.
- 2) Follow-up methods: outpatient follow-up, telephone follow-up and review of relevant medical records.
- 3) Outcome measures:

**① Primary end point:** progression of DKD. Progression of DKD was defined as renal failure (requiring transplantation or dialysis, or persistent eGFR <15 ml/min/1.73 m^2) or a persistent decline of 30% in eGFR from baseline.

**② Secondary End Points:** I. Cardiogenic Death: Death caused by cardiac disease or related complications. II. Major Adverse Cardiovascular Events (MACE): Including major cardiovascular events such as myocardial infarction, stroke, and unstable angina. III. Kidney Transplantation: Successful cases of kidney transplantation surgery. IV. Hypoglycemic Events: Record the frequency and severity of hypoglycemia occurrences.

#### **(4) 16S RNA Sequencing Analysis and Non-Target Metabolic Analysis**

We performed 16S rRNA sequencing, non-target metabolic analysis, and inflammatory factor detection on collected fecal and blood samples to compare differences in gut microbiota, metabolites, and inflammatory factors across different prognostic groups, and to identify prognostic markers. We also compared the differences in gut microbiota, metabolites, and inflammatory factors among patients with high glycemic variability, intermediate glycemic variability, and low glycemic variability. Furthermore, we identified gut microbiota markers and serum metabolic markers associated with high glycemic variability.

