## **III. RESEARCH OBJECTIVES**

**3.1 Main objective:** To explore the relationship between glycemic variability, gut microbiota metabolites and prognosis of patients with DKD.

**(1) Study subjects:** patients with diabetic nephropathy.

**(2) Exposed factors:** glycemic variability (assessed by continuous glucose monitoring CGM); gut microbiota, serum metabolites (assessed by 16S rRNA high-throughput sequencing technology and serum non-targeted liquid chromatography-mass spectrometry LC-MS) and inflammatory factors.

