### 3.2.2 Characteristics of Gut Microbiota and Serum Metabolites in Different GV Groups and Their Correlation With Prognosis

- (1) **Study subjects:** patients with diabetic nephropathy
- (2) **Exposure factors:** different glycemic variability (GV) groups.
- (3) **Study outcome:** characteristics of intestinal microbiota and serum metabolites.
- (4) **Specific objectives:** Through 16S rRNA high-throughput sequencing technology and serum non-target liquid chromatography -Mass Spectrometry (LC-MS) was used to investigate the characteristics of intestinal microflora and serum metabolites in patients with different glycemic variability (GV) groups. The relationship between the bacterial co-abundance groups (CAG) and the functional modules of serum metabolites was further established to explore their correlations with glycemic variability and poor prognosis.

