#### 4.1.3. Gut Microbiota and Serum Metabolites in DKD Patients with Different Blood Glucose Variability Groups and Their Correlation with Prognosis

(1) Patients with DKD were divided into high GV group and low GV group according to GV status, and the intestinal microbiota characteristics and serum metabolites characteristics of patients in different GV groups were analyzed.

(2) Based on the association between gut microbiota, serum metabolic biomarkers and prognosis, the relationship between the bacterial co-abundance group (CAG) and the functional modules of serum metabolites was further established to explore their correlation with glycemic variability and poor prognosis.

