## 5.4 Methods for Determining the Required Sample Size for Research

This exploratory study investigates the impact of gut microbiota and related metabolites on prognosis in diabetic kidney disease (DKD) patients. To achieve this, patients will be divided into two groups based on adverse prognosis outcomes, with subsequent comparisons of gut microbiota and metabolite differences between groups. To minimize microbial variations caused by individual differences, each group requires at least 30 participants, meaning there must be at least 30 patients with adverse prognosis events. Drawing from existing research, a 2023 study published in *\*Diabetes Care\** [Diabetes Care.2023;46(4):868-873.] included 975 DKD patients with an average follow-up of 4.7 years, reporting 156 major outcomes of DKD progression. Consequently, the total sample size was calculated as  $975/156*30=187.5$ . Considering potential dropouts and incomplete responses, we typically increase the sample size by 10%, ultimately enrolling 210 patients as the modeling cohort. Additionally, 60 DKD patients were included as a validation cohort. During actual recruitment, sample size adjustments may be made based on factors such as recruitment speed and data quality. Regular assessments of sample adequacy should also be conducted to ensure statistical power.

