### 5.8.2 Statistical Analysis

Descriptive statistical analysis was performed on the collected data. Continuous variables were presented as mean  $\pm$  standard deviation (or median and interquartile range), while categorical variables were expressed as frequency and percentage. For intergroup comparisons of continuous variables, independent samples t-test or Mann-Whitney U-test was selected based on data normality. In cases involving multiple group comparisons, one-way ANOVA or Kruskal-Wallis test was employed. Categorical variable comparisons utilized chi-square test or Fisher's exact test to assess significant differences between groups. To evaluate relationships among multiple variables, linear regression was applied to continuous variables, logistic regression to categorical variables, and Cox proportional hazards regression to time-to-event data. These analyses adjusted for potential confounders such as age, sex, disease duration, and baseline glucose levels to ensure result accuracy and reliability. Confounding factors were included in regression analyses to minimize their impact. Additionally, propensity score matching was used to balance baseline characteristics between groups, ensuring comparability and enhancing the internal validity of the study results.

After adjusting for various covariates, we examined the association between adverse prognosis, hyperglycemic variability, and the gut microbiota  $\alpha$ -diversity index. The relationship between hyperglycemic variability, adverse prognosis, and  $\beta$ -diversity differences was tested using genus-level Bray-Curtis distance-based permutation ANOVA (PERMANOVA). Using MaAsLin, we identified gut microbiota communities potentially associated with adverse prognosis and hyperglycemic variability by comparing hyperglycemic variability groups with hypoglycemic variability groups, and prognostic favorable groups with unfavorable groups. OPLS-DA was employed to identify target metabolites potentially related to hyperglycemic variability and adverse prognosis, with adjustments made through linear regression. Mediation analysis was conducted to evaluate whether gut microbiota metabolism might mediate the association between hyperglycemic variability and adverse prognosis. Sensitivity analysis was performed to test the robustness of the mediation effect.

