**9. Expected Progress and Completion Date of the Research Project**

Total duration of the project implementation	4 years
--	---------

Annual Plan Arrangements	
Schedule	Key contents and outcomes of the stage objectives
July 2025-May 2026	
Main content of the stage goal:
 
① Patient recruitment and enrollment  (2025.7-2025.12): Eligible subjects were recruited according to the inclusion and exclusion criteria in the protocol and enrolled.
 
② Glucose monitoring and sample collection  (2025.7-2025.12): CGM monitoring was performed for 14 days in enrolled patients, and stool and blood samples were collected. Ensure that the collection, preservation, and transportation of samples met relevant standards and requirements to provide high-quality samples for subsequent analysis.
 
③ Preliminary data analysis (2026.1-2026.5): The collected CGM data were preliminarily analyzed, patients were divided into different groups according to blood glucose variability, and preliminary data analysis report was completed.
 
④ Follow-up Initiation (2026.1-2026.5): A follow-up protocol and team were established to conduct a 3-year observation period for participants. Regular collection of clinical data—including diabetic kidney disease (DKD) progression, major adverse cardiac events (MACE), quality of life assessments, and complication occurrences—provided essential follow-up data for subsequent predictive model development. The follow-up program was successfully initiated and implemented.
 
⑤ Additional patient recruitment  (2026.1-2026.5): Start additional recruitment of patients in a validation cohort for validation of the prediction model.
 
Achievement
 
 
① The recruitment of patients was completed, and the enrollment rate reached the target.
 
② The collection rate of samples was 100%.
 
③ The preliminary data analysis report was completed.
 
④ The follow-up program was initiated and proceeded smoothly.
 
⑤ additional patients were recruited and the enrollment rate was as planned.
 

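### Section 4.1.3 splits patients into two GV groups and section 5.5(4) into three; section 5.8.2 does not settle which applies, and continuous GV would avoid the choice.

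*Protocol*

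**What the plan says.** Three places in the protocol say something about the number of GV groups.

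- Section 4.1.3 has two groups: "Patients with DKD were divided into high GV group and low GV group according to GV status".
- Section 5.5(4) has three. Microbiota, metabolites and inflammatory factors are compared among patients with "high glycemic variability, intermediate glycemic variability, and low glycemic variability".
- Section 5.8.2 identifies taxa with MaAsLin by "comparing hyperglycemic variability groups with hypoglycemic variability groups", which I read as high against low GV. The same section carries a general sentence: "In cases involving multiple group comparisons, one-way ANOVA or Kruskal-Wallis test was employed". That sentence is not tied to GV.

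Two further places leave the number open. Secondary purpose 3.2.2 gives the exposure as "different glycemic variability (GV) groups", and the timetable in section 9 says that "patients were divided into different groups according to blood glucose variability". The main objective (3.1) lists "glycemic variability (assessed by continuous glucose monitoring CGM") as an exposure without saying that it is split. No section presents the three-group comparison as an additional or sensitivity analysis.

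**The concern.** A missing cut-off is something a statistical analysis plan (SAP) can supply, and its absence is not the point here. The difficulty is that two sections define different groups. A SAP that adopts either one will depart from a section of the protocol.

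The number of groups decides who counts as high or low and whether a middle group exists. It also decides whether the test has one or two degrees of freedom. With both groupings in the protocol and no order between them, the reported result can depend on which is used. Section 9 schedules grouping by GV in preliminary analyses before the final association analysis, so the choice could be made with data in hand.

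The comparison directly affected is secondary purpose 3.2.2. In section 5.8.2 the term hyperglycemic variability also enters the alpha-diversity, PERMANOVA, OPLS-DA and mediation analyses. The text does not say whether it means a group or a measured value there, so the conflict may reach those analyses too.

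**Working it through.** **1. Does the sample size settle the number of groups?** Section 5.4 gives 975/156 × 30 = 187.5. Adding 10% gives 206.25 (207); dividing by 0.90 gives 208.3 (209). Both are within 3% of the stated 210, so that figure reproduces. The rule that "each group requires at least 30 participants" refers to groups defined by prognosis, not by GV. The 210 therefore neither depends on the number of GV groups nor decides it.

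**2. Can the sections be read together?** Section 4.1.3 divides the patients into two groups with nobody left over, so these cannot be the outer thirds of a three-way split. It conflicts directly with section 5.5(4). The high-against-low MaAsLin contrast in 5.8.2 could be the two groups of 4.1.3 or the outer groups of 5.5(4). The ANOVA/Kruskal-Wallis sentence could serve three GV groups but does not say so. Section 5.8.2 fits both readings.

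**3. How many patients change role?** Assume equal-sized groups, since no cut-offs are given, and the modelling cohort of 210.

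- Two groups: 210/2 = 105 and 105.
- Three groups: 210/3 = 70, 70 and 70.
- Patients who leave high or low for intermediate: 70, that is 35 from each side.

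If all 270 patients were used, the number would be 270/3 = 90.

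**4. What does an open choice do to the error rate?** In null simulations with n = 210, one normal metric and one normal marker, I took the smaller p-value from the median-split t-test and the tertile ANOVA. It falls below 0.05 in about 8.5% of runs, against 5% for either test alone.

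**5. How much information does each split keep?** Assume a roughly normal GV metric and a linear relation with the marker.

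- Median split: 2/π = 0.637, and 210 × 0.637 ≈ 134 patients' worth of continuous data.
- Equal thirds: the share of GV variance between groups is (2/3) × (φ(0.431)/(1/3))² = 0.793. An unordered ANOVA spends two degrees of freedom to use it, so power is the fair comparison.

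**6. Power at r = 0.20**, n = 210, two-sided 5%:

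- Continuous, Fisher z: Φ(atanh(0.20) × √207 − 1.96) = Φ(2.917 − 1.96) = 83%.
- Median split: the correlation becomes 0.20 × √0.637 = 0.160, and Φ(atanh(0.160) × √207 − 1.96) = Φ(0.356) = 64%.
- Three-group ANOVA: R² = 0.04 × 0.793 = 0.0317 and noncentrality 210 × 0.0317/(1 − 0.0317) = 6.88 on 2 and 207 degrees of freedom, giving 64%.

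| r | Continuous | Median split | Three-group ANOVA |
|---|---|---|---|
| 0.15 | 58% | 41% | 39% |
| 0.20 | 83% | 64% | 64% |
| 0.25 | 96% | 83% | 85% |
| 0.30 | 99% | 94% | 96% |

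The two groupings are about equally powerful, and both fall below continuous GV.

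**The case against.** The best defence is that this is a wording slip in a study that section 5.4 calls exploratory. Comparison by GV group is a secondary purpose. The main objective does not split GV, the prediction model uses a GV index, and section 5.8.2 provides tests for two groups and for more than two. The protocol also looks for an optimal GV control target; if the true relation has a threshold, the loss from grouping would differ from the figures above.

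Much of this stands and limits the point. Several stronger readings that a reader might infer are not supported:

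- *The core comparison of the study is contradictory.* The conflict is documented for 3.2.2. Its reach into the diversity and mediation analyses rests on an ambiguous term, and no section says that GV is split in the Cox model.
- *Section 5.8.2 is a second two-group plan.* Its MaAsLin contrast is equally consistent with the outer groups of three.
- *Three groups keep 79% of the information, like 167 patients.* That holds for linearly scored thirds, not for the ANOVA that the protocol names.
- *The error rate reaches 10% or 29%.* The 10% needs an extra test of the extreme thirds, which the protocol does not plan. The 29% comes largely from choosing among four metrics at an assumed correlation of 0.7. One fixed median split across those four already gives 16%, and they are listed only as background in section 2.1.2.
- *Few events make the split costly here.* The conflicting comparison is of baseline markers by GV group and uses all patients.

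The objection does not remove the conflict between 4.1.3 and 5.5(4), which no other section resolves.

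**Conclusion.** The contradiction holds: section 4.1.3 has two GV groups, section 5.5(4) has three, and section 5.8.2 does not decide between them. It bears on secondary purpose 3.2.2 with certainty, and on the diversity and mediation analyses only possibly.

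The role change assumes equal-sized groups. The 8.5% also assumes that the more favourable of the two groupings is reported, which nothing in the protocol says will happen; it measures the opening left, not a prediction. The information and power losses assume a roughly normal metric and a linear relation, and a threshold relation would change them. Under those assumptions neither grouping is the better one to keep for inference, which is the argument for continuous GV. This should be corrected, but it does not invalidate the design.

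**What to change.** Name one CGM metric as the GV exposure. Enter it as a continuous variable in the alpha-diversity, PERMANOVA, MaAsLin, metabolite and mediation models, and check non-linearity in the marker models.

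In the Cox model, enter it as a single linear term without splines, because events are few. Section 5.4 aims for 30. Its own rate of 156/975 = 16% over 4.7 years, rescaled to the 3-year follow-up at a constant hazard, gives 1 − 0.84^(3/4.7) = 10.5%, or about 22 events in 210 patients.

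Keep one grouping, for description only, with the same number of groups in 4.1.3, 5.5(4) and 5.8.2. State in 5.8.2 whether hyperglycemic variability means the continuous metric or membership of the high group.

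The cost is wording only, since 14 days of CGM are already planned for every patient. The one real drawback is that OPLS-DA needs classes. For GV it must use the single grouping or be replaced by OPLS regression.

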#### **(5) Construction and Evaluation of Forecasting Model**

First, feature screening was performed using LASSO regression to select variables from five aspects: demographic characteristics, baseline scales, gut microbiota and non-target metabolites, and peripheral blood inflammatory biomarkers. Nine machine learning algorithms were employed to construct classification models, with performance evaluated through resampling training/verification mechanisms. The optimal model was selected via 10-fold cross-validation and performance metrics. Model performance and applicability were assessed using AUROC curves, calibration curves, Brier scores, and decision analysis plots. During training, validation, and testing phases of the optimal model, five-fold cross-validation and learning curves were used to evaluate model fit and stability. Finally, SHAP package was utilized to generate SHAP explanation plots to determine the importance and contribution of individual features.

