#### 4.1.4 Construction and validation of adverse event prediction model for DKD patients

(1) Based on the screening of the predictive factors related to adverse events in DKD prognosis, including glycemic variability index, related clinical indicators, intestinal flora, serum metabolites, inflammatory factors, etc., the predictive model was established by using machine learning algorithm, and the performance and stability of the model were evaluated.

(2) independent cohorts of patients with DKD were added as validation cohorts to evaluate the performance and stability of the predictive model.

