Based on baseline data, gut microbiota, serum metabolites, and inflammatory factors, predictive models will be constructed using machine learning algorithms (e.g., random forests, support vector machines, neural networks). Feature selection methods (e.g., LASSO regression, recursive feature elimination) will be employed to identify the most prognostic features, thereby enhancing model accuracy and interpretability. Internal stability of the models will be assessed through 10-fold cross-validation, while their generalization ability will be validated using independent validation cohorts.

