January 2028-December 2028	
Main content of the stage goal:
 
① Follow-up Data Organization and Analysis: Conduct comprehensive final organization and analysis of collected follow-up data to ensure data integrity and accuracy. Perform statistical analysis to evaluate patient outcomes, including disease progression, major adverse cardiac events (MACE), quality of life assessment, and complication occurrence. Complete the follow-up data analysis report.
 
② Association Analysis: By integrating glycemic variability grouping results, this study investigates the relationship between gut microbiota characteristics and serum metabolite profiles with clinical outcomes, including disease progression, major adverse cardiovascular events (MACE), quality of life, short-term complications, and overall prognosis. Through correlation analysis and multiple regression analysis, we aim to uncover underlying biological mechanisms and predictive biomarkers, ultimately producing a comprehensive association analysis report.
 
③ Prediction Model Development: By integrating multi-dimensional data including baseline information, gut microbiota profiles, serum metabolite profiles, and inflammatory factors, we constructed predictive models using machine learning algorithms such as random forests, support vector machines, and neural networks. Through cross-validation and other optimization methods, we enhanced the model's predictive performance and stability, completing the initial development of the prediction model.
 
④ Model evaluation and validation: Appropriate evaluation metrics were used to assess the constructed prediction model, verifying its generalization capability and predictive performance across different datasets. Based on the evaluation results, the model was further optimized and adjusted to ensure reliability and practicality, and the model evaluation report was completed.
 
Achievement :
 
 
① The follow up data analysis report was completed.
 
② Complete the association analysis report.
 
③ The preliminary construction of the prediction model was completed.
 
④ The model evaluation report was completed.
 

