January 2029-July 2029	
Main content of the stage goal:
 
① Clinical Validation of the Model: Validate the predictive model using additional recruited patients to evaluate its practical value and feasibility in real-world clinical settings. Based on validation results, make necessary adjustments and improvements to the model. This will facilitate its clinical application and promote its adoption, providing scientific evidence for prognostic assessment and personalized treatment of diabetic kidney disease (DKD) patients. The process will culminate in the completion of a clinical validation report.
 
② Complete the project: write the paper and complete the project report. Results:
 
 
① The clinical validation report was completed.
 
② The final report was completed, and the relevant academic papers were written and published.
 

------------------------	--

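### LASSO screening listed ahead of cross-validation makes the internal AUROC and Brier score optimistic if run in that order, and a model adjusted after validation has no independent check

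*Protocol*

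**What the plan says.** **Order of model building.** Section 5.5 (5) begins: "First, feature screening was performed using LASSO regression to select variables from five aspects". Model fitting comes next: "Nine machine learning algorithms were employed to construct classification models, with performance evaluated through resampling training/verification mechanisms". Then: "The optimal model was selected via 10-fold cross-validation and performance metrics". AUROC, calibration, Brier score and decision curves describe the result. The section also mentions a testing phase without saying where it falls relative to the screening. Section 4.1.4 gives the same order: the model is built "Based on the screening of the predictive factors related to adverse events in DKD prognosis", and its performance is evaluated afterwards.

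**Internal and external validation.** Section 5.8.2 says: "Internal stability of the models will be assessed through 10-fold cross-validation, while their generalization ability will be validated using independent validation cohorts". It names LASSO and recursive feature elimination as example selection methods but does not place them inside the folds. Section 5.4 defines one modelling cohort of 210 and one validation cohort: "Additionally, 60 DKD patients were included as a validation cohort".

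**Changes after evaluation.** In section 9, the row for January to December 2028 says: "Based on the evaluation results, the model was further optimized and adjusted to ensure reliability and practicality", after evaluation on data sets it does not name. The row for January to July 2029 validates the model in the additionally recruited patients and continues: "Based on validation results, make necessary adjustments and improvements to the model. This will facilitate its clinical application and promote its adoption". Only the paper and the project report follow.

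**The concern.** There are two separate problems.

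**A. Screening before resampling.** LASSO uses the outcome. If it is run once on all modelling patients, each patient later held out in a fold has already influenced which features are in the model. Cross-validation then measures only the refitting of coefficients on features known to fit those same patients. The figures can make a model that is no better than quoting the event rate look useful, and one of nine algorithms is picked on them.

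**B. Adjustment after the only validation.** Once the model is changed in the light of the 60 patients' results, those patients no longer test it independently. The changed version is the one the timetable links to clinical adoption, yet the independent validation promised in section 5.8.2 does not cover it.

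**Working it through.** **The plan's own figure.** Section 5.4: 975/156 × 30 = 187.5; with 10% added, 187.5 × 1.10 = 206.25, enrolled as 210. This reproduces to within 2%. The protocol states no AUROC, Brier score or allowance for optimism.

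**Event counts.** Section 5.4 gives 156/975 = 0.16 over a mean of 4.7 years; section 5.5 (3) gives 3 years of follow-up. Under a constant hazard the 3-year risk is 1 − (1 − 0.16)^(3/4.7) = 0.105.
- Modelling cohort: 210 × 0.16 = 33.6, about 34; 210 × 0.105 = 22.1, about 22.
- Validation cohort: 60 × 0.16 = 9.6, about 10; 60 × 0.105 = 6.3, about 6.
- Brier score from quoting the event rate for everyone, p(1 − p): 22/210 gives 0.094; 34/210 gives 0.136.

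**A. Simulation of the listed order.** Assumptions, none of them fixed by the protocol: 210 patients; 22 or 34 events; 100 or 500 Gaussian candidates, independent or correlated 0.5 in blocks of 20; no signal, or five features shifted by 0.5 SD; LASSO penalty by 10-fold cross-validation at minimum error or by the one-standard-error rule. That is 2 × 2 × 2 × 2 × 2 = 32 settings. A lightly ridge-penalised logistic model was fitted to the selected features and assessed by stratified 10-fold cross-validation. An empty selection scored AUC 0.50 and Brier p(1 − p). The truth came from 4000 new patients. There were 231 replicates per setting (77 for in-fold screening); the Monte Carlo SE of the excess was 0.002 to 0.013.

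Excess = cross-validated AUC − AUC of the same model in new patients:

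| Penalty rule | Signal | AUC excess | CV Brier below true Brier | Runs selecting nothing |
|---|---|---|---|---|
| Minimum error | None | 0.097–0.178 | 0.008–0.069 (both signal cases) | – |
| Minimum error | Five features | 0.125–0.242 | as above | – |
| One SE | None | 0.004–0.030 | 0.000–0.006 | 90–99% |
| One SE | Five features | 0.055–0.117 | 0.009–0.033 | 4–75% |

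- The mean excess was positive in all 32 settings.
- Under the one-standard-error rule with signal, runs that selected at least one feature had an excess of 0.106 to 0.245.
- At minimum error, in 15 of 16 settings the cross-validated Brier score beat quoting the event rate while the true one was worse than that.
- Screening inside each fold gave an AUC within 0.04 of the truth in all 32 settings.
- Example (500 independent candidates, 22 events, signal, minimum error): AUC 0.818 against a true 0.576, excess 0.242; Brier 0.064 against a true 0.106 and 0.094 with no model. Under the one-standard-error rule: 0.592 − 0.529 = 0.063, with 74% of runs empty.

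A second simulation used a different pipeline: pure noise, 189 patients (210 less 10%), logistic LASSO keeping up to ten features. Screening first gave AUC 0.77, 0.84 and 0.88 for 100, 300 and 1000 candidates with 30 events, and 0.87 for 300 candidates with 20 events; in new data all were about 0.50. Screening inside the folds gave 0.52, 0.53, 0.50 and 0.49. With 30 events, the screen-first Brier score was 0.115, 0.100 and 0.088, against 0.155 to 0.166 in new data and 0.134 with no model.

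**B. Re-scoring an adjusted model on the same 60 patients.** Assumptions: 6 or 10 events; locked model's true AUC 0.70.
- Recalibration only: AUC unchanged; Brier 0.0825 against 0.0878 in new patients (6 events) and 0.1259 against 0.1312 (10 events), about 0.005 too low.
- Re-choosing among nine equally good variants (score correlation 0.8 to 0.9): apparent AUC 0.755–0.774 (6 events) or 0.746–0.761 (10 events), against 0.70.
- Adding the best of ten uninformative predictors: apparent 0.815 against a true 0.628 (6 events); 0.780 against 0.637 (10 events).

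**The case against.** **In-fold screening is not ruled out.** This is true, and a statistical analysis plan might settle it. But the protocol is not merely silent. It puts screening first in section 5.5 (5), repeats that order in section 4.1.4 and nests it nowhere, so a team following the text would get the biased figures. Part A is therefore conditional on the listed order being followed.

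**The independent cohort protects the conclusion.** This stands for the leak in A: if screening is confined to the 210 modelling patients, the 60 give an honest test of the model as it stood before adjustment. What remains is a misleading internal estimate and a possibly poor choice of algorithm. The external test is also imprecise: by the Hanley–McNeil formula, an AUC of 0.75 in 60 patients has a 95% half-width of about 0.23 (6 events) or 0.19 (10 events).

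**The size is assumed.** This stands. Candidate count, penalty, signal and correlation are all assumptions, and the two simulations differ in size. The second keeps about ten features, while the one-standard-error rule often keeps none. The event counts borrow the progression rate, although section 3.2.1 names all-cause death as the model's primary end point, and the main simulation makes no allowance for the planned 10% loss. Neither simulation includes the choice among nine algorithms. The direction does not depend on these points.

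**Adjustment may not happen, and updating is ordinary practice.** Both are fair, and recalibration alone does little harm. The point applies only if changes are made. The protocol then names no further patients and gives the updated model no separate status.

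**The 2028 adjustment precedes complete validation outcomes.** Validation patients recruited in January to May 2026 and followed for 3 years finish in 2029, so only interim outcomes could be used in 2028. This narrows the risk, but the text does not exclude it.

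**Conclusion.** Both parts hold. Under the listed order the internal AUROC and Brier score are optimistic: by roughly 0.10 to 0.24 in AUC for a penalty at minimum cross-validation error, and by anything from almost nothing to about 0.12 under the one-standard-error rule. These ranges illustrate the assumed settings; they do not forecast this study's bias.

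The 60-patient result is a valid assessment of the model before adjustment, provided the 2028 optimisation did not use those patients. A version adjusted afterwards has no independent assessment, and how far a re-scored AUC would mislead runs from nil for recalibration to a gap of 0.14 to 0.19 if a chance predictor is added (0.780 − 0.637 and 0.815 − 0.628). Confidence is medium, because the protocol leaves the pipeline details open. The matter should be settled before model building starts in 2028.

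**What to change.** 1. In sections 5.5 (5) and 5.8.2, state that LASSO or recursive feature elimination, tuning and the choice of algorithm are all repeated within the training part of each resample, by nested cross-validation or bootstrap optimism correction of the whole pipeline. Report that estimate as the internal performance.
2. In the 2028 and 2029 rows of section 9, state that the model is locked before the validation outcomes are opened and that the 2028 evaluation data exclude the validation cohort. Report the locked model's AUC, calibration and Brier score, with confidence intervals, as the validation result. Label any later adjustment as an updated model not yet externally validated.

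The cost is wording in four places and more computing time; no extra patients or data are needed. The reported internal performance will be lower, or about the same under a strict penalty, and an adjusted model could not be presented as validated.
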